11.0 TOXICITIES/SIDE EFFECTS

In each arm standard SBRT will be used delivering 40 Gy in 5 fractions to the prostate and seminal vesicles and patients will be randomized to receive 6 months of ADT using Degarelix monthly injections or SBRT alone without ADT. ADT administration is routine and its side effect profile well recognized and established. Side effects of ADT (Degarelix) include hot flashes, fatigue, weight gain, loss of libido, muscle tone decrease and gynecomastia. These side effects generally reverse 6-12 months after cessation of ADT. Any urinary or rectal toxicity that is grade 3 or higher will be considered an adverse event.

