4.2 Intervention

Eligible patients with intermediate risk disease will be randomized to ADT with SBRT versus SBRT alone. The ADT patients will be treated with monthly degarelix injections. After three months (+/- 1 month) have elapsed, these patients as per routine would undergo fiducial marker placement followed by simulation and SBRT to follow. For this cohort ADT will continue until 6 months of Degarelix is administered. If a patient develops an allergic reaction to the Degarelix injection, he may be switched to Leuprolide acetate monthly injections in its place.

For patients treated with SBRT alone referral will be made for fiducial marker placement with simulation and SBRT to follow. Patients will then be followed at 6 month intervals with routine serum PSA and testosterone testing. All patients will undergo a post-SBRT standard 12 core prostate biopsy at 24-30 months after completion of SBRT to evaluate local tumor control status.

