9.0 TREATMENT/INTERVENTION PLAN

Androgen Deprivation Therapy Arm: Within two weeks prior to the first injection, patients will obtain routine blood tests including CBC and liver function tests and testosterone levels. Degarelix injections will be administered in the radiation oncology clinics monthly. The first injection is administered as a boost, 240 mg given as two subcutaneous injections of 120 mg at a concentration of 40 mg/mL which is then followed by 80 mg given as one subcutaneous injection at a concentration of 20 mg/mL every 28 days (+/- 7days). In 10% of patients a skin rash could develop at the injection site. If this is noted and symptomatic for the patient the injection could be switched to monthly Lupron intramuscular injections (7.5.mg).

Study treatment: Stereotactic, Ultra-Fractionated Radiotherapy (same for each arm)

Intensity-modulated, image-guided, ultra-hypofractionated external beam radiotherapy will incorporate prostate and seminal vesicles and this planning target volume will receive 8 Gy x 5 fractions. As per routine for intermediate risk patients, the lymph nodes will not be included within the treatment portal.

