10.0 EVALUATION DURING TREATMENT/INTERVENTION

10.1 Evaluation during Treatment

- Patient completion of study specific PRO assessments
 - EPIC-26
 - SF-12
 - IPSS

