10.2 Evaluation during Follow-Up

- Physical exam
- Performance status
- Clinical evaluation for late urinary, rectal toxicity and sexual dysfunction per standard CTCAE assessments and grading.
- PSA
- Serum Testosterone
- EPIC – 26
- SF-12
- IPSS
- Prostate biopsy, 24-30 months post SBRT

Table 1. Schedule of assessments

	Pre-Treatment	During Radiation Therapy	Follow up
	Within 8 weeks prior to study randomization	Within 2 week prior to the initiation of Degarelix ¹	
Informed consent	X		
Medical history	X		
Physical exam	X		X
Digital rectal exam	X		
Performance status	X		X
Histologic or pathologic confirmation of disease	X ²		
MRI prostate/pelvis within 6 months of randomization	X ³		
Bone scan within 6 months of randomization if determined necessary	X		
EPIC-26	X	X ⁴	X
SF-12	X	X ⁴	X
IPSS	X	X ⁴	X
PSA	X	X	X
CBC	X	X	
Comp	X	X	
Liver function tests	X	X	
Serum testosterone	X	X	X
Toxicity assessment			X
Degarelix		X ⁵	
Fiducial marker placement		X ⁶	
Radiation therapy		X'	
Biopsy			X ⁸

1. For patients randomized to the ADT + SBRT arm
2. Histologic or pathologic confirmation of disease can be done anytime prior to randomization.
3. CT of the pelvis with contrast may be performed if MRI is contraindicated.
4. To be completed during treatment, at the 3rd of 5th fraction of later
5. Degarelix will be given monthly (+/- 7 days), 3 months before and 3 months after radiation therapy.
6. Fiducial markers will be placed 3 days before simulation.
7. Radiation therapy will be given every other day.
8. Prostate post-treatment biopsy will be performed once at 24-30 months post SBRT.

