17.2 Serious Adverse Event (SAE) Reporting

An adverse event is considered serious if it results in ANY of the following outcomes:

- Death
- A life-threatening adverse event
- An adverse event that results in inpatient hospitalization or prolongation of existing hospitalization
- A persistent or significant incapacity or substantial disruption of the ability to conduct normal life functions
- A congenital anomaly/birth defect
- Important Medical Events (IME) that may not result in death, be life threatening, or require hospitalization may be considered serious when, based upon medical judgment, they may jeopardize the patient or subject and may require medical or surgical intervention to prevent one of the outcomes listed in this definition

Note: Hospital admission for a planned procedure/disease treatment is not considered an SAE.

SAE reporting is required as soon as the participant signs consent. SAE reporting is required for 30-days after the participant's last investigational treatment or intervention. Any events that occur after the 30-day period and that are at least possibly related to protocol treatment must be reported.

If an SAE requires submission to the IRB office per IRB SOP RR-408 'Reporting of Serious Adverse Events', the SAE report must be sent to the IRB within 5 calendar days of the event. The IRB requires a Clinical Research Database (CRDB) SAE report is submitted electronically to the SAE Office as follows:

For IND/IDE trials: Reports that include a Grade 5 SAE should be sent to [contact]. All other reports should be sent to [contact].

For all other trials: Reports that include a Grade 5 SAE should be sent to [contact]. All other reports should be sent to [contact].

The report should contain the following information:

Fields populated from CRDB:

- Subject's initials
- Medical record number
- Disease/histology (if applicable)
- Protocol number and title

Data needing to be entered:

- The date the adverse event occurred
- The adverse event
- The grade of the event
- Relationship of the adverse event to the treatment (drug, device, or intervention)
- If the AE was expected
- The severity of the AE
- The intervention
- Detailed text that includes the following
 - A explanation of how the AE was handled
 - A description of the subject's condition
 - Indication if the subject remains on the study
- If an amendment will need to be made to the protocol and/or consent form
- If the SAE is an Unanticipated Problem

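### Beyond SAE reporting and quality-of-life questionnaires, the plan has no systematic grading, recording or between-arm comparison of non-serious harms of degarelix, the only randomised difference

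*Combined protocol and SAP*

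**What the plan says.** **Definition.** Section 11.0 states: "Any urinary or rectal toxicity that is grade 3 or higher will be considered an adverse event". It is the only explicit rule on what counts as a non-serious adverse event. The same paragraph describes the drug's profile: "Side effects of ADT (Degarelix) include hot flashes, fatigue, weight gain, loss of libido, muscle tone decrease and gynecomastia".

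**Assessment.** During treatment, Section 10.1 lists one item, "Patient completion of study specific PRO assessments", with EPIC-26, SF-12 and IPSS beneath it. In follow-up, Section 10.2 lists "Clinical evaluation for late urinary, rectal toxicity and sexual dysfunction per standard CTCAE assessments and grading".

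**Known drug reactions.** Section 9.0: "In 10% of patients a skin rash could develop at the injection site". Section 4.2: "If a patient develops an allergic reaction to the Degarelix injection, he may be switched to Leuprolide acetate monthly injections in its place". Neither section says that the reaction or the switch is recorded.

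**Serious events.** Section 17.2 begins: "An adverse event is considered serious if it results in ANY of the following outcomes". Its list of outcomes has no organ limit, reporting starts at consent, and the report asks how the event relates to treatment, including the drug.

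**Data and analysis.** The data list in Section 16.0 names demographics, patient-reported outcomes, PSA, testosterone and biopsy results, with no adverse event item. Section 2.0 has no toxicity objective and Section 14.0 has no safety analysis. Section 14.0 does compare quality-of-life scores between arms.

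**The concern.** A randomised comparison of SBRT with and without ADT should be able to show what the added drug costs the patient as well as what it gains. Here the explicit adverse event rule and most of the clinician grading concern bladder and bowel, the organs exposed to the radiation that both arms share. The effects that the plan itself attributes to degarelix fall outside that rule.

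If the trial finds fewer positive biopsies with ADT, readers will want to weigh that against graded harms by arm. Followed as written, the plan would supply serious event reports, quality-of-life scores and late urinary, rectal and sexual grades. It would not supply a systematic account of non-serious drug reactions or of drug switches.

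**Working it through.** This is mainly a comparison of sections, with a small count for scale.

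**1. Do the plan's own drug effects meet its adverse event rule?**
- Section 11.0 names six ADT effects. None is urinary or rectal, so none meets the rule.
- The injection-site rash (Section 9.0) and the allergic reaction (Section 4.2) do not meet it either.
- Loss of libido overlaps with sexual dysfunction, which is CTCAE-graded in follow-up. The other five effects have no scheduled clinician grading.

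**2. Is there clinician grading while the drug is being given?**
- Exposure, from footnote 5 of Table 1: "Degarelix will be given monthly (+/- 7 days), 3 months before and 3 months after radiation therapy".
- Section 10.1 schedules questionnaires only. Footnote 4 places them once, at the third fraction or later.
- Follow-up visits are 6-monthly (Sections 1.0 and 4.2). I assume they are counted from SBRT. With SBRT at month 3, the first graded visit falls at 3 + 6 = month 9 after the first injection, which is 9 − 6 = 3 months after ADT ends.
- Section 4.2 allows ±1 month on the timing of SBRT. That gives months 8 to 10, or 2 to 4 months after a 6-month course ends.
- If visits were counted from the start of ADT instead, the first would fall at about month 6, as the course ends.
- On either reading, apart from SAE reporting, no clinician toxicity assessment is scheduled before about the end of the course. The toxicity row of Table 1 appears to agree, but the conclusion rests on the text of Sections 10.1 and 10.2.

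**3. Is the term used consistently?**
- Section 11.0 ties it to two organ systems and a grade.
- Section 13.0 allows removal for an unacceptable adverse event related to the intervention, with no organ limit.
- Section 17.2 defines seriousness by outcome, also with no organ limit.
- The three uses do not match.

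**4. Scale.**
- Section 14.0 plans 200 evaluable patients plus 10%: 200 / (1 − 0.10) = 222.2, rounded up to 223. This reproduces the stated total.
- ADT arm at 1:1: 223 / 2 = 111.5, about 111.
- Rash at the plan's 10%: 0.10 × 111 = 11.1, about 11 patients. Among 100 evaluable patients it is 0.10 × 100 = 10.
- The plan gives no rates for the other effects, so they cannot be counted.

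**The case against.** The strongest reply is that Section 11.0 is an inclusion rule. It says that certain toxicities are adverse events, and does not say that nothing else is. This stands. A reader might infer that adverse events are defined solely as grade 3+ urinary or rectal toxicity, so that a serious drug event elsewhere would not count at all and the number of such events would be zero by definition. The documents do not support that inference. Section 13.0 uses the term without an organ limit. Section 17.2 lists outcomes such as congenital anomaly that cannot be urinary or rectal, runs from consent through the whole ADT period, and asks about relationship to the drug. Serious drug harms are reportable.

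A reader might also infer that ADT effects go unmeasured. That is too strong as well. Section 3.3 frames the harm of ADT as its effect on quality of life, and the plan measures quality of life: EPIC-26 has Hormonal and Sexual domains (Section 5.0), and Section 14.0 compares the arms at each survey. Sexual dysfunction is CTCAE-graded. Section 11.0 says that ADT effects generally take 6 to 12 months to reverse, so some would still be present at the first follow-up visits, which include a physical exam.

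The Section 16.0 list may not be exhaustive, since it omits even the toxicity grades that Section 10.2 requires. The institutional monitoring plans cited in Section 16.2 are not reproduced and may add requirements.

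These replies narrow the point but do not remove it. As Section 5.0 describes them, the questionnaires cover urinary, bowel, sexual, hormonal and general health function. None is described as capturing injection-site reactions, allergic reactions or drug switches. Nothing in the text supplies graded non-serious events during ADT, or a table by arm.

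**Conclusion.** The point holds in a limited form. Outside SAE reporting and the questionnaires, non-serious harms of the only randomised component have no stated grading schedule while the drug is given, no stated recording rule and no between-arm comparison. Late sexual dysfunction is a partial exception, because it is graded in follow-up.

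The only size that the plan allows is about 11 of about 111 ADT patients with an injection-site rash and no rule for recording it. This takes the plan's 10% at face value and assumes that these rashes are mostly non-serious; the plan gives no grade for them.

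The primary biopsy comparison, its power and its type 1 error are unaffected. This is a worthwhile, inexpensive improvement to the safety information and does not threaten the trial's main conclusion.

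**What to change.** - **Section 11.0:** define as a recorded adverse event (a) any CTCAE grade 3+ event in any organ system, (b) the ADT effects already listed there, and injection-site or allergic reactions, at any grade, and (c) any event recorded as the reason for a change or stop of degarelix. Part (b) is needed because a rule limited to grade 3+ could miss most of the rashes and listed effects. Use the same starting point in both arms, either consent (as in Section 17.2) or randomisation.
- **Sections 10.1 and 10.2:** add toxicity grading at the SBRT visits, and widen the grading at the existing 6-monthly visits to match the definition.
- **Section 16.0:** add adverse events to the data list.
- **Section 14.0:** add a table of adverse events by arm, based on visits that both arms attend. Only the ADT arm has injection visits, so comparing arms on events found there would build in unequal ascertainment. Report those events descriptively for the ADT arm.
- **Sections 11.0, 13.0 and 17.2:** reconcile the use of the term adverse event.

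This concerns recording only and leaves the rules for treating patients or switching drug as they are. The cost is protocol wording, one extra form, and modest data entry at visits that already take place.

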12.0 CRITERIA FOR THERAPEUTIC RESPONSE/OUTCOME ASSESSMENT

For the primary endpoint of this study, post-SBRT prostate biopsies will be performed to assess local tumor control for each of the treatment arms. While post-SBRT biopsies performed outside of MSKCC are permitted for the study, the central pathology review will be performed by the MSKCC pathology department. For the central pathology review, please send the study patients' post-SBRT prostate biopsy slides the address listed in the laboratory manual in appendix IV.

As has been well established criteria for the assessment of post-radiation biopsies (10), post-treatment biopsies will be categorized as negative if there is no evidence of adenocarcinoma, positive if there is evidence of adenocarcinoma (which could be assigned a Gleason score), or treatment effect ,where adenocarcinoma is noted displaying severe treatment effect precluding the assignment of a Gleason score. In our experience this latter classification is associated with a clinical behavior more consistent with a negative biopsy.

Biochemical recurrence will be determined according to the established Phoenix criteria of 2 ng/dL elevation of the PSA nadir level (nadir + 2 definition). Distant metastases will be defined as patients with imaging evidence or biopsy-proven metastatic disease in distant sites outside of the prostate most commonly in bone. Therefore the cumulative incidence of biochemical failure and distant failure will be computed by setting the starting time as the beginning date of the treatment until the event of interest, with death without the event of interest as the competing risk. Overall survival is defined from the beginning date of the treatment until death.

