14.0 BIOSTATISTICS

The primary objective of this phase III trial is to compare 2-year biopsy positivity rate of intermediate risk prostate cancer patients treated with SBRT + short course ADT versus SBRT alone. The 2-year biopsy positivity rate will be calculated in each arm as a proportion of patients whose 2-year (from the end of SBRT) biopsy result is positive over patients who have 2-year biopsy results examined or whose 2-year biopsy results are regarded as positive (see the replacement rule below). We plan to analyze an evaluable sample of 200 patients, randomized in a 1:1 ratio to the two arms. This sample size has a power greater than 0.90 and type 1 error rate of 0.05 if the true 2-year biopsy positivity rates are 35% and 15% respectively, for the two arms using a two-sided, two-sample proportion test. This test will also be adjusted for the randomization stratification variables. Patients who died due to disease within 2 years from the end of SBRT will be regarded as having a positive biopsy. Patients who died not due to disease or are lost to follow-up within 2 years from the end of SBRT without any sign of progression will be replaced. To this end we will enroll an additional 10% patients upfront so the total sample size is 223. However, only the first 200 evaluable patients will be counted towards the primary endpoint. One interim analyses and one final analysis are planned (using equal spacing of looks) and the null hypothesis that the two arms have the same 2-year biopsy positivity rates will be rejected at these two looks if the p-values are <0.003 and <0.049, respectively, based on the Lan-DeMets alpha spending function approach. We expect that 100 patients will be enrolled each year, 50 from MSK and 50 between all regional sites. Therefore we anticipate to complete the enrollment in 2-3 years, plus an additional 2-year mandatory follow-up.

For the secondary objectives, the cumulative incidence rates of biochemical failure and distant failure will be evaluated by the competing risks method and Gray's test will be used to compare the two arms. Overall survival rates will be estimated by Kaplan-Meier method and compared by log-rank tests. QOL outcomes will be summarized and tabulated. Results from the two arms will be compared by Wilcoxon rank sum tests at time points when these surveys are conducted. All patients will be analyzed for the secondary objectives.

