15.2 Randomization

Patients will be randomized to receive ADT+SBRT, or SBRT alone. Immediately after consent is obtained, the RSA at MSKCC will register participants in the Clinical Trials Management System (CTMS). Once the participant's eligibility is established the registration will be finalized and the participants will be randomized using the Clinical Research Database (CRDB). Randomization will be accomplished by the method of random permuted block, and will be stratified by favorable vs unfavorable intermediate risk. After the treatment

arm is determined by randomization, the RSA will notify physicians at MSKCC of the treatment arm and participant ID via email within 24 hours of randomization.

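### Section 12 does not state that the central biopsy review is masked to arm, and Section 14 does not state how a treatment-effect biopsy is counted

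*Combined protocol and SAP*

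**What the plan says.** Section 12.0 makes the post-SBRT biopsy the primary endpoint. Biopsies may be taken outside the institution, but "the central pathology review will be performed by the MSKCC pathology department". There are three categories:

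- *negative*: no adenocarcinoma;
- *positive*: adenocarcinoma that could be given a Gleason score;
- *treatment effect*: "where adenocarcinoma is noted displaying severe treatment effect precluding the assignment of a Gleason score".

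The section adds that, in the institution's experience, the third category behaves more like a negative biopsy.

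Section 14.0 puts patients with a positive result in the numerator and also counts disease deaths within two years of SBRT as positive. It does not mention *treatment effect*.

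On allocation, Section 4.2 gives one arm monthly degarelix and the other arm no injection, and no placebo is described. Section 15.2 says that "the RSA will notify physicians at MSKCC of the treatment arm and participant ID via email". The supplied text says nothing about masking of pathologists, coded slides or requisitions, dual reading or adjudication. The laboratory manual (Appendix IV), to which Section 12.0 refers for sending slides, is listed by title only.

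**The concern.** A biopsy that contains cancer is a failure if it is called *positive*. If it is called *treatment effect*, Section 12.0 suggests that it is not a failure. The boundary is a judgement about how altered the cells look. A reader who knows that a patient had hormone therapy has one more reason to attribute the changes to treatment, and a reader who knows that he did not has one fewer. If that knowledge affects the call, it affects the sole primary endpoint differently in the two arms.

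The missing counting rule adds to the problem. If *treatment effect* is classed as positive or not positive only after results are known, the same set of reads can give two different primary results.

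**Working it through.** **Inputs from the documents.** Section 14.0 plans an "evaluable sample of 200 patients, randomized in a 1:1 ratio to the two arms", so 100 per arm. The rates are 35% (SBRT alone) and 15% (ADT + SBRT), tested "using a two-sided, two-sample proportion test", with a final threshold of p<0.049.

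**The plan's own figures.** Section 14.0 states: "This sample size has a power greater than 0.90 and type 1 error rate of 0.05". With mean rate 0.25:

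power = Φ{[0.20·√100 − 1.96·√(2·0.25·0.75)] / √(0.35·0.65 + 0.15·0.85)} = Φ{(2.000 − 1.200)/0.596} = Φ(1.342) = 0.910.

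Exact binomial enumeration of the pooled z test gives 0.914. Total enrolment is 200/0.9 = 222.2, rounded up to 223, as stated. Both figures reproduce, and this point does not touch them.

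**Assumption.** The documents give no rate of arm-dependent reading. Let a share m of ADT-arm positives be read as *treatment effect* and counted as not positive. The arms are truly equal at rate p, so the observed ADT-arm rate is p(1 − m). The true rates of 25% and 35% are also chosen for illustration: 35% is the planned control rate and 25% is the midpoint of 35% and 15%.

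**Method.** Exact enumeration of two binomials with n = 100 each, rejecting when the two-sided pooled z test gives p<0.049. The interim look and the stratification adjustment are ignored.

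| True rate, both arms | Shift m | Observed ADT-arm rate | Chance of falsely favouring ADT | Chance of any rejection |
|---|---|---|---|---|
| 25% | 0 | 25.0% | 2.4% | 4.9% |
| 25% | 10% | 22.5% | 6.0% | 6.8% |
| 25% | 20% | 20.0% | 13.0% | 13.2% |
| 35% | 0 | 35.0% | 2.4% | 4.8% |
| 35% | 10% | 31.5% | 7.4% | 8.0% |
| 35% | 20% | 28.0% | 18.3% | 18.4% |

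**In counts.** The test statistic is z = (x₁ − x₂)/100 ÷ √[p̄(1 − p̄)·2/100].

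- From 35 against 35, moving 13 ADT-arm biopsies gives 35 against 22. Then p̄ = 0.285, z = 0.13/0.0638 = 2.04 and p = 0.042. Moving 12 is not enough (p = 0.061).
- From 25 against 25, moving 12 gives 25 against 13. Then p̄ = 0.19, z = 0.12/0.0555 = 2.16 and p = 0.031.

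Reading alone would have to move 13/35 = 37% or 12/25 = 48% of ADT-arm positives to turn exactly equal counts into a significant result. Smaller shifts act by adding to chance differences, as the table shows.

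**Opposite direction.** Suppose instead that 10% or 20% of SBRT-alone positives were read as *treatment effect* under the planned 35% against 15%. The control rate would become 31.5% or 28%, and power would fall from 0.91 to 0.79 or 0.61.

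**The case against.** A reader might infer that the central pathologists are unmasked. The documents do not say so. The notice of allocation in Section 15.2 goes to physicians and does not mention pathologists. Coding rules for slides could be in the laboratory manual, which is not in the supplied text. What stands is that Section 12.0, which defines the endpoint, does not state masking.

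A reader might also infer that any bias must favour ADT. The documents do not support a direction. Both arms receive the same 8 Gy x 5, so every reader has reason to expect radiation change in every patient. ADT ends about 3 months after SBRT and the biopsy is at 24–30 months, which leaves some 21–27 months between them. Section 3.3 states the case for and against adding ADT. These facts weaken the mechanism but do not remove it, because the call remains a judgement and Section 4.1 expects the lower positive rate with ADT.

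It would also go too far to say that no later analysis could help. Counting *treatment effect* as positive cancels any movement between those two categories, and the categories are already recorded. A later masked re-read is conceivable. Neither is planned.

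There are existing safeguards. One department applies established criteria to all slides, including those from outside, and disease deaths count as positive without a reader. Central review gives consistency, which is not the same as masking.

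Finally, Section 17.0 treats the biopsy as routine care, so a clinical report is needed as well. That is a practical constraint on how the masked call is recorded.

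**Conclusion.** The point holds as an omission. In a trial that is open label in effect, the plan does not state that the review deciding the primary endpoint is masked, and it does not state how one of the three biopsy categories is counted. Arm knowledge could bias the comparison; whether it would, by how much and in which direction cannot be derived from the documents.

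The error rates in the table are illustrations. They rest on the assumed 10% and 20% shifts, on true rates of 25–35%, on *treatment effect* counting as not positive, and on a single final test without the interim look or stratification adjustment. On those terms a 10% shift does modest harm and a 20% shift does substantial harm. The stated design figures stand. The change is worth making because it is cheap and protects the only primary endpoint.

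**What to change.** 1. In Section 12.0 and the laboratory manual, state that the planned central review is done on slides and requisitions that do not show arm or ADT history. State that the central call is the one used for the endpoint for all biopsies, wherever they were taken.
2. In Section 14.0, state that *treatment effect* counts as not positive in the primary analysis, in line with Section 12.0.
3. Add one sensitivity analysis that counts *treatment effect* as positive. It shows whether the conclusion depends on that boundary.

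The cost is the coding of slides and requisitions, and care to keep arm information out of the central read. Where one reading of an in-house biopsy also serves the clinical report, the endpoint call can be recorded before any ADT history is shown. No extra reader, procedure or patient is required. The sample size stays at 200 evaluable and 223 in total, and power stays at 0.91. If the laboratory manual already provides for masking, a sentence in Section 12.0 saying so meets the masking part of item 1.

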4.0 OVERVIEW OF STUDY DESIGN/INTERVENTION

4.1 Design

For this proposed Phase III study, intermediate risk patients will be randomized to received 6 months of ADT which would be given 3 months prior to planned SBRT to the prostate and 3 months during/following SBRT. ADT will be administered via Degarelix monthly injections. SBRT will be delivered with a prescription dose of 8 Gy x 5 prescribed to the planning target volume. Inter-fraction motion targeting and target position correction will be utilized as is routine in our department during the treatment SBRT.

The primary end-point of this study is the proportion of patients who have positive 2-year post-treatment prostate biopsies. Based on our previous published experience, we expect that the 2-year rate of a positive biopsy using ADT with ultra-hypofractionated SBRT for intermediate risk features would be 15% compared to 35% for those patients treated with SBRT alone. We anticipate we would require powering the study with 100 patients in each arm. Randomization will be stratified by favorable-intermediate and unfavorable-intermediate risk status (unfavorable-intermediate risk will be defined as patients having Gleason 4+3, >50% positive biopsy cores or 2 intermediate risk factors combined such as Gleason 7 and PSA > 10 ng/ml).

The primary endpoint is the 2-year biopsy which is generally scheduled at the end of the second year. However, we have provided some flexibility as to prevent prospective and retrospective deviations. Therefore, we have chosen to allow the primary endpoint biopsy to occur between 24-30 months which we believe is reasonable based on our clinical experience.

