6.0 CRITERIA FOR SUBJECT ELIGIBILITY

6.1 Subject Inclusion Criteria

- Biopsy proven intermediate risk prostate cancer, which includes patients with any one of the following variables:
 - Gleason 7 disease
 - PSA 10-20 ng/ml
 - Clinical T2b-T2c disease

Note: Patients who only have radiographic evidence of T3 disease (i.e. extracapsular extension, or seminal vesical invasion radiographically) will not be excluded.

- Serum testosterone \geq 240 ng/dL determined within 2 months prior to enrollment
- At least 4 weeks must have elapsed from major surgery
- KPS \geq 80%
- Prostate size as determined on MRI to be $<$ 90 cc. Prostate size can be determined on CT scan if MRI is not available.
- 18 years of age or older
- IPSS \leq 20
- Patient must be available for follow-up. After 2 years of follow-up following post-treatment biopsy, telephone-based follow-up will be acceptable
- Laboratory test findings within 8 weeks of randomization:
 - Adequate hepatic function with serum bilirubin \leq 1.5 times the upper institutional limits of normal (ULN), ALT and AST \leq 2.5 x ULN. Patients with a history of Gilbert's syndrome may be enrolled if the total bilirubin is $<$ 3 mg/dL with a predominance of indirect bilirubin
 - Adequate renal function with serum creatinine \leq 1.5 x ULN
 - Adequate hematologic function with absolute neutrophil counts \geq 1,500 cell/mm³ and platelets \geq 100,000 cells/mm³ and hemoglobin value \geq 9 g/dL (Note: patients whose anemia has been corrected to a hemoglobin value \geq 9 g/dL with blood transfusions are allowed)

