16.0 DATA MANAGEMENT ISSUES

A Research Study Assistant (RSA) will be assigned to the study. The responsibilities of the RSA include project compliance, data collection, abstraction and entry, data reporting, regulatory monitoring, problem resolution and prioritization, and coordinate the activities of the protocol study team.

The data collected for this study will be entered into Medidata RAVE. Source documentation will be available to support the computerized patient record. All research material from this study will be handled with the same confidentiality as patient's other medical data. Data collected will include participant demographics, PRO outcomes data, PSA and testosterone values, and biopsy results.

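### Section 12.0 gives the biochemical-failure threshold in ng/dL, 100 times below nadir + 2 on the ng/ml scale the protocol uses for its other PSA values

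*Combined protocol and SAP*

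**What the plan says.** Section 12.0 sets biochemical recurrence by the "Phoenix criteria of 2 ng/dL elevation of the PSA nadir level (nadir + 2 definition"). The rise is thus described three ways in one sentence: by a named criterion, by a number with a unit, and by a label that has no unit of its own.

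PSA carries a unit in two other places. The example of combined risk factors in the stratification rule of Section 4.1 is "Gleason 7 and PSA > 10 ng/ml". The eligibility list in Section 6.1 gives a PSA range of 10 to 20, also in ng/ml. The only other value in ng/dL is the testosterone criterion in Section 6.1, "240 ng/dL determined within 2 months prior to enrollment".

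Section 14.0 uses the outcome without restating the threshold: "the cumulative incidence rates of biochemical failure and distant failure will be evaluated by the competing risks method and Gray's test" will compare the two arms. Section 2.0 names biochemical failure among the secondary objectives.

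**The concern.** The number and unit in Section 12.0 do not agree with the label beside them once that label is read on the protocol's own PSA scale. No other section states the threshold, so nothing elsewhere overrides it.

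What is at stake is the event definition for one formally tested secondary outcome. Someone who programs the endpoint from the text as written would record a failure at a rise of 0.02 ng/mL above nadir. Cumulative incidence in both arms would then reflect very small PSA movements. The two arms might or might not be affected alike, and the documents do not allow that to be judged. Section 16.0 lists "PSA and testosterone values, and biopsy results" among the data collected. That passage shows no confusion of units, but with two serum markers recorded side by side, and ng/dL being the protocol's unit for testosterone, the PSA unit should be explicit and correct.

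**Working it through.** **Inputs**

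- Threshold as written: a rise of 2 ng/dL, labelled nadir + 2 (Section 12.0).
- PSA unit elsewhere: ng/ml (Sections 4.1 and 6.1; these are the only two other PSA values with a unit).
- Other use of ng/dL: testosterone, 240 ng/dL (Section 6.1).

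**Step 1. Convert the written threshold.** 1 dL = 100 mL, so x ng/dL = x/100 ng/mL.

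2 ng/dL = 2/100 = 0.02 ng/mL.

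**Step 2. Convert the label on the protocol's PSA scale.** Nadir + 2 in ng/mL is a rise of 2 ng/mL.

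2 ng/mL = 2 × 100 = 200 ng/dL.

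**Step 3. Compare.** 2 / 0.02 = 100, or equally 200 / 2 = 100. The stated figure of 2 ng/dL is not reproduced from the label; it is exactly 100 times too small.

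**Step 4. Look for a correcting statement.** Section 14.0 names the outcome and the test but gives no threshold. Sections 2.0, 3.3, 10.2 and 16.0 mention biochemical outcomes or PSA without one. Section 12.0 is the sole definition.

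**Step 5. Check whether the design figures depend on it.** Section 14.0 claims power above 0.90 at a type 1 error of 0.05, for assumed positivity rates of 35% in one arm against 15% in the other, with 200 evaluable patients split 1:1. With 100 per arm and a mean rate of (0.35 + 0.15)/2 = 0.25:

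- standard error under the null: √(2 × 0.25 × 0.75 / 100) = 0.0612
- standard error under the alternative: √((0.35 × 0.65 + 0.15 × 0.85) / 100) = 0.0596
- power = Φ[(0.20 − 1.96 × 0.0612) / 0.0596] = Φ(1.34) = 0.910

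The enrolment total is 200 / (1 − 0.10) = 222.2, rounded up to 223. Both stated figures reproduce, and neither uses a PSA value.

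**What cannot be computed.** The documents give no nadir or follow-up PSA values, so neither the number of patients reclassified nor any difference between arms can be stated. A comparison with the eligibility range of 10 to 20 ng/ml would not help, because that is a pretreatment range and failure is measured from the post-treatment nadir.

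**The case against.** The strongest reply is that the sentence corrects itself. It adopts a named, established criterion and repeats it as nadir + 2, so the governing rule is the criterion and the unit is a one-letter typing error that an informed reader would pass over. Nothing in the documents suggests that anyone would apply 0.02 ng/mL. The case report form, which is not among the documents, may already hold PSA in ng/mL. PSA is recorded as a value, so the endpoint could be recomputed with no loss of data. And nadir + 2 has no unit, so reading it in ng/mL is an inference from two other values.

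Most of this stands, and it limits the weight of the point. The intended value is recoverable and no effect on results has been shown. It does not make the text right. The only unit attached to the label is the one that conflicts with the rest of the protocol, and an endpoint definition should not depend on the reader overriding it. The inference to ng/mL rests on every other PSA value in the documents that has a unit, few though they are.

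One reassurance needs care. No section ties the PSA threshold to the primary biopsy endpoint. However, the replacement rule in Section 14.0 turns on the absence of any sign of progression, and progression is not defined there. The documents neither link that phrase to PSA nor exclude it. This is not evidence of an effect on the primary analysis.

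**Conclusion.** The concern holds. The biochemical-failure threshold in Section 12.0 is 100 times below nadir + 2 on the protocol's own PSA scale: 0.02 ng/mL as written, against 2 ng/mL. The conclusion assumes only that nadir + 2 is meant in the unit used for the other PSA values, and the labels in the same sentence support that reading.

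The error is confined to the definition of one secondary outcome. The sample size, the power and the interim boundaries do not use it, and no section explicitly connects it to the primary endpoint. The effect on event counts is unknown. It should be fixed because it is a wrong decision threshold in the only definition of a tested outcome, but it is a minor correction.

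**What to change.** In Section 12.0, replace ng/dL with ng/mL, so that the number, the unit and the nadir + 2 label agree with one another and with Sections 4.1 and 6.1. Then confirm that the case report form and the analysis code hold PSA in ng/mL and apply the threshold in that unit.

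The cost is one unit changed in an amendment and one check of the database and code. Data collection, sample size and the primary analysis are unchanged. If any biochemical failures have already been derived with the literal threshold, they can be recomputed from the recorded PSA values.
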